**Protocol Template** 

Sponsor: Menarini Pharmaceutical Study Code: MEIN/19/ZoNe-HYP/001 Protocol Version\_1 of 16/07/2020

# **Summary of Changes from Previous Version**

Affected	Summary of Revisions Made	Rationale
Section(s)		
	N/A	First emission

Identification Number: FORM-000050125

Previous Doc Number: CTWI10A

Version Number: 1.0, CURRENT

Sponsor: Menarini International Operations Luxembourg Study Code: MEIN/19/ZoNe-HYP/001

Protocol Version\_1 of 16/07/2020

# **Protocol Template**

Sponsor: Menarini Pharmaceutical Study Code: MEIN/19/ZoNe-HYP/001	Protocol Version_1 of 16/07/2020

**Identification Number:** FORM-000050125

**Previous Doc Number:** CTWI10A

> **Version Number:** 1.0, CURRENT

Sponsor: Menarini International Operations Luxembourg Study Code: MEIN/19/ZoNe-HYP/001

Protocol Version\_1 of 16/07/2020

# 2. PROTOCOL SYNOPSIS

Title	Open-label, multicenter, multinational interventional clinical trial to
	assess effectiveness and safety of the extemporaneous combination of
	nebivolol and zofenopril calcium in grade 1 to 2 hypertensive patients
	versus each monotherapy
Sponsor Study Code	MEIN/19/ZoNe-HYP/001
Study product, Dosage	Extemporaneous combination of nebivolol (NEB) 5 mg tablets (Anatomical
and Regimen:	Therapeutic Chemical [ATC] code: C07AB12) with zofenopril calcium (ZOF)
-Investigational Product	30 mg tablets (ATC code: C09AA15)
	This is a phase IV, open-label, multicenter, multinational study with 2 study
	periods (a run-in period of 4 weeks and an assessment period of 8 weeks).
	Grade 1-2 hypertensive patients (blood pressure [BP] ranging from ≥140/90
	mmHg to ≤179/109 mmHg) on treatment with any angiotensin converting
	enzyme-inhibitors (ACE-i) or beta blockers (BBs) including ZOF 30 mg or
	NEB 5 mg respectively will be screened for eligibility (Visit 1).
	On the same day, the eligible patients will enter into a run-in period after
0	Screening, during which:
Study Type and Design	Patients on ZOF 30 mg or NEB 5 mg will continue the same therapy
	for 4 weeks
	Patients on any other ACE-i will be assigned to monotherapy with
	ZOF 30 mg while patients on any other BB will be assigned to
	monotherapy with NEB 5 mg, respectively, for 4 weeks
	After the 4 weeks of monotherapy in the run-in period, if BP at Visit 2,
	remains uncontrolled (sitting SBP/DBP >130/80 mmHg) despite an
	adherence to the treatments ranging from 80% to 120%, the patients will

Identification Number: FORM-000050125

Previous Doc Number: CTWI10A

Version Number: 1.0, CURRENT

## **Protocol Template**

Sponsor: Menarini Pharmaceutical Study Code: MEIN/19/ZoNe-HYP/001

Protocol Version\_1 of 16/07/2020

	start treatment (Week 0, Visit 2) with the extemporaneous combination of
	NEB 5 mg/ZOF 30 mg (NEB/ZOF) and will be assessed for further 8 weeks
	(assessment period).
	If the patients, at Visit 2 after the Run-In period, have controlled BP (sitting
	SBP/DBP ≤130/80 mmHg), and/or do not tolerate the treatment, and/or do
	not maintain the adherence to the therapy (range from 80% to 120%), these
	patients will not be continued further in the study.
	At the end of the assessment period (Visit 3) the antihypertensive effect of
	the extemporaneous combination of NEB 5 mg and ZOF 30 mg will be
	evaluated. A total number of 290 patients will be screened considering 25%
	of drop-out rate, to obtain approximately 216 completed patients at the end
	of the study.
Phase	IV
	Primary objective:
	To assess the antihypertensive effect of the extemporaneous
	combination of NEB 5 mg and ZOF 30 mg in lowering sitting DBP
	after 8 weeks of treatment, in patients with uncontrolled BP who were
	previously treated with NEB or ZOF monotherapies for at least 4
	weeks
	Secondary objectives:
Objectives	To assess the antihypertensive effect of the extemporaneous
	combination of NEB 5 mg and ZOF 30 mg in lowering sitting SBP
	after 8 weeks of treatment in patients with uncontrolled BP, after at
	least 4 weeks of treatment with NEB or ZOF monotherapies
	To evaluate the total number and percentage of patients who
	achieved the BP goal (sitting BP ≤130/80 mmHg) at Visit 2 and
	Visit 3
	To assess compliance to the monotherapy and extemporaneous

Identification Number: FORM-000050125

Previous Doc Number: CTWI10A

Version Number: 1.0, CURRENT

#### **Protocol Template**

Sponsor: Menarini Pharmaceutical Study Code: MEIN/19/ZoNe-HYP/001

Protocol Version\_1 of 16/07/2020

# combination (actual doses taken versus planned doses to be taken) To evaluate the safety and tolerability of the ZOF and NEB monotherapies, and the extemporaneous combination of NEB 5 mg and ZOF 30 mg after 8 weeks of treatment **Exploratory objective:** To assess the antihypertensive efficacy at different time points in patients who (1) received NEB or ZOF monotherapies before the run-in period, (2) received any other ACE-i or BB monotherapies before the run-in period To assess the antihypertensive effect on patients, based on their hypertension grade, presence or absence of hypercholesterolemia, presence or absence of diabetes at Visit 2 and Visit 3 Primary endpoint: Change in mean sitting DBP between Week 0 (Visit 2) and Week 8 (Visit 3) Secondary endpoint: Change in mean sitting SBP between Week 0 (Visit 2) and Week 8 (Visit 3) Total number and proportion of patients achieving the BP goal (sitting BP ≤130/80 mmHg) at Week 0 (Visit 2) and Week 8 (Visit 3)

### **Endpoints**

- Adherence to treatment will be measured through treatment compliance which is 100 × (actual doses taken versus planned doses to be taken) from Visit 1 to Visit 2 for the monotherapies and from Visit 2 to Visit 3 for the extemporaneous combination
- Safety and tolerability of the NEB and ZOF monotherapies, as well as extemporaneous combination between NEB 5 mg and ZOF 30 mg will be measured by adverse events (AEs), SAEs, AEs of special interest (AEOSI), vital signs, physical examination,

Identification Number: FORM-000050125

Previous Doc Number:
CTWI10A

Version Number: 1.0, CURRENT

#### **Protocol Template**

Sponsor: Menarini Pharmaceutical Study Code: MEIN/19/ZoNe-HYP/001

Protocol Version\_1 of 16/07/2020

electrocardiogram (ECG), and concomitant medications at Week 0 (Visit 2) and Week 8 (Visit 3)

### Exploratory endpoint:

- Change in mean sitting SBP and DBP between Visit 1 and Visit 2:
   (a) in the group of patients who were on ZOF 30 mg and NEB 5 mg at Visit 1 and continued on the same treatment until Visit 2 and (b) in the group of patients, who switched to ZOF 30 mg or NEB 5 mg from any other ACE-i or BB at Visit 1 until Visit 2.
- Change in mean sitting SBP and DBP between Visit 1 and Visit 3: (a) in the group of patients who were on ZOF 30 mg and NEB 5 mg at Visit 1 and continued on the same treatment until Visit 2 and (b) in the group of patients who switched to ZOF 30 mg or NEB 5 mg from any other ACE-i or BB at Visit 1 until Visit 2.
- Number and proportion of patients achieving the BP goal (sitting BP ≤130/80 mmHg) at Visit 2 and Visit 3 evaluated in the patients: (a) who were on ZOF 30 mg and NEB 5 mg at Visit 1 or (b) who switched to ZOF 30mg or NEB 5 mg from any other ACE-i and BB at Visit 1
- Number and proportion of patients, divided in subgroups based on the hypertension grade, the presence or absence of diabetes, the presence or absence of hypercholesterolemia achieving the BP goal (sitting BP ≤130/80 mmHg) at Visit 2 and Visit 3

Study Population: Patients characteristics Number of Patients Approximately, 290 male or female Caucasian uncontrolled hypertensive patients between ≥18 and <65 years of age, who are on treatment with ZOF or NEB, or, on any other ACE-i or BBs, for at least 1 month, will be screened for eligibility.

A total drop-out rate of 25% from Visit 1 to Visit 3, has been considered. A

Identification Number: FORM-000050125

Previous Doc Number:
CTWI10A

Version Number: 1.0, CURRENT

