#### **EXPLORATORY**

- To assess the antihypertensive efficacy at different time points in patients who (1) received NEB or ZOF monotherapies before the run-in period,
- Change in mean sitting SBP and DBP between Visit 1 and Visit 2:
   (a) in the group of patients who were ZOF 30 mg and NEB 5 mg at Visit 1 and continued on the

Evaluation of the antihypertensive efficacy of monotherapies and combination therapy in patients with different CV risk

Identification Number: FORM-000050125

Previous Doc Number:
CTWI10A

Version Number: 1.0, CURRENT

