#### 8.1.1. Inclusion Criteria

- Male or female Caucasian uncontrolled hypertensive patients ≥18 and <65 years of age (see definition in criterion 3), in monotherapy either with ACE-i or BBs since at least 1 month, at Screening
- 2. Patients are able to understand and have freely given written informed consent at Screening
- Patients with mean sitting SBP ≥140 mmHg and ≤179 mmHg and/or mean sitting DBP
   ≥ 90 mmHg and ≤109 mmHg at Screening
- 4. Patients who are able to comply with all study procedures and who are available for the duration of the study
- 5. Ability to take oral medication and willing to adhere to the drug regimen
- 6. A female patient of childbearing potential is eligible to participate if she is not pregnant, or not breastfeeding. A woman is considered fertile following menarche and until becoming postmenopausal unless permanently sterile. Women of childbearing potential

Identification Number: FORM-000050125

Previous Doc Number:
CTWI10A

Version Number: 1.0, CURRENT

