#### 7.1. ADJUSTMENTS FOR COVARIATES AND FACTORS TO BE **INCLUDED IN ANALYSES**

No adjustment for covariates will be performed for this study.

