#### 16.3.2. ANALYSIS OF EXPLORATORY EFFICACY VARIABLES

Exploratory efficacy variables will be summarized in a descriptive manner using safety population for Visits 1, 2 and 3.

- Change in mean sitting SBP and sitting DBP between Visit 1 and Visit 3 will be analyzed as following:
- Change from baseline in sitting SBP and DBP from prior (Visit 1) and post (Visit 3) combination therapy will be compared using paired t-test. The p-value will be presented using a paired t-test comparing mean at baseline and mean at Week 8. The exploratory endpoint will be presented in a descriptive manner using n, mean, median, SD, Q1, Q3, and minimum and maximum. Assumption of normality will be investigated using Wilk-Shapiro test. If violation is observed, then paired t-test will be replaced by Wilcoxon signed rank test.
- The number of patients achieving BP goal (sitting BP ≤130/80 mmHg) will be summarized for Visit 2 and Visit 3, along with percentage. A p-value using exact McNemar's test will be presented to compare the proportion of patients achieving the BP goal (sitting BP ≤130/80 mmHg) between Visit 2 and Visit 3.
- The number of patients achieving BP goal (sitting BP ≤130/80 mmHg) will be summarized for Visit 2 and Visit 3, along with percentage for each of the subgroup specified under section 7.5 of the SAP.

Document: \\ieedc-vnasc01\BIOSdata\Menarini\NebZof\KZA41200\Biostatistics\Documentation\SAP

Author: [name] Version Number: Final V1.0

Version Date: [14Dec2021]

Template No.: CS TP BS016 Revision 6 Reference: CS WI BS005

Page 28 of 37

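### The Visit 1 to Visit 2 blood pressure change is filed under efficacy although one group stays on its existing drug; no switched-minus-continued contrast is planned, and the analysis population is conditioned on Visit 2 blood pressure

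*Protocol*

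**What the plan says.** The exploratory objective (protocol synopsis and section 6; SAP 2.3) begins "To assess the antihypertensive efficacy at different time points in patients who (1) received NEB or ZOF monotherapies before the run-in period" and then names patients who had received any other ACE-i or BB. The justification column in protocol section 6 gives the purpose of these endpoints as "Evaluation of the antihypertensive efficacy of monotherapies and combination therapy in patients with different CV risk" factors.

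The first endpoint is the Visit 1 to Visit 2 change in sitting SBP and DBP in two groups:

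- group (a), the continuing patients: "in the group of patients who were on ZOF 30 mg and NEB 5 mg at Visit 1 and continued on the same treatment";
- group (b), the switched patients: those "who switched to ZOF 30 mg or NEB 5 mg from any other ACE-i or BB at Visit 1 until Visit 2".

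Everyone enters "in monotherapy either with ACE-i or BBs since at least 1 month, at Screening" (protocol 8.1.1), with SBP of 140 to 179 and/or DBP of 90 to 109 mmHg at Visit 1. For the run-in, the synopsis says: "Patients on ZOF 30 mg or NEB 5 mg will continue the same therapy".

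On analysis, SAP 16.3.2 says: "Exploratory efficacy variables will be summarized in a descriptive manner using safety population for Visits 1, 2 and 3". Protocol 14.5.5 says the same. The only exploratory change in blood pressure given a test is Visit 1 to Visit 3, by a within-patient paired t-test. Continued versus switched is not among the subgroup factors in protocol 14.5.6 or SAP 7.5. The table in protocol 14.4 assigns these endpoints to the Enrolled population, not the safety population.

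**The concern.** A before-and-after change estimates the effect of a drug only if the drug starts between the two readings. In group (a) it does not: the patient takes ZOF 30 mg or NEB 5 mg before Visit 1 and still takes it at Visit 2. Because a high Visit 1 reading is an entry condition, some fall is expected at Visit 2 with no drug effect at all. Closer supervision and lifestyle counselling can add to it.

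Group (b) carries drift of the same kind plus whatever the switch does, and its own summary cannot separate the two. Group (a) is the only concurrent reference for that drift, and the plan does not set it against group (b). A report written to this plan could present drift as efficacy of ZOF or NEB in both groups.

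**Working it through.** **1. The plan's own figures.** Neither document gives a figure for the run-in endpoint. The nearest is the sample size in protocol 14.2: SD 10 mmHg for the DBP change, assumed change 4, null 2, power 90%, 5% level. With a one-sided test, (10 × (1.645 + 1.282) / (4 − 2))² ≈ 214, and the t-based calculation gives 216 with power 0.901. So 216 reproduces. It is used below only as a source for N and the SD; this point does not alter it.

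**2. What each change contains.**

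- Group (a): change = drift(a).
- Group (b): change = drift(b) + switch effect.
- (b) − (a) = switch effect + [drift(b) − drift(a)].

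Drift here means regression to the mean plus participation effects. Only the third line removes drift common to both groups, and it is not in protocol 14.5.5 or SAP 16.3.2.

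**3. Size of the drift.** The documents give no usual pressures or visit-to-visit variability, so these inputs are assumptions:

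- usual on-treatment BP from 138/86 to 148/90 mmHg;
- between-patient SD 12/8;
- visit-to-visit SD from 6/4 to 10/7;
- SBP–DBP correlation 0.5.

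Model: reading = usual BP + independent visit error, with no drug effect at either visit. A patient enters if Visit 1 SBP ≥140 or DBP ≥90, with both below 180/110. Nine scenarios (three levels of usual BP by three of visit SD) give these mean Visit 1 to Visit 2 changes:

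| Patients analysed | DBP, mmHg | SBP, mmHg |
|---|---|---|
| All enrolled | −0.4 to −2.2 | −0.8 to −3.7 |
| Safety population, either component above 130/80 at Visit 2 | −0.3 to −1.5 | −0.7 to −2.6 |
| Safety population, both components above | −0.1 to +0.9 | −0.4 to +0.5 |

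A rerun reproduced all three rows. At the upper visit SD, the implied SD of an unselected DBP change is 7 × √2 = 9.9 mmHg, close to the plan's 10.

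**4. The population.** The safety population (SAP 5.3) requires a dose of the combination, which is given only if Visit 2 BP is uncontrolled. The Visit 1 to Visit 2 change is then conditioned on its own endpoint. The second and third rows of the table show the result: with no drug effect, the size and even the sign of the mean depend on the filter. SAP 3.3 recognises the same selection when it notes that the proportion at goal at Visit 2 will always be zero. The documents do not say whether >130/80 means either or both components, and I take no position on that.

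**5. Precision of switched minus continued.** Half-width = 1.96 × SD × √(1/n_a + 1/n_b). The SD is 10 mmHg, borrowed from the Visit 2 to Visit 3 DBP change, and N = 216. The split is not given, so a range is shown.

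- 108:108: 1.96 × 10 × √(1/108 + 1/108) = 2.7 mmHg
- 54:162: 1.96 × 10 × √(1/54 + 1/162) = 3.1 mmHg
- 22:194: 1.96 × 10 × √(1/22 + 1/194) = 4.4 mmHg (4.5 at 21:195)

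These are unadjusted. Using 290 would be optimistic, because that is the number screened and protocol 14.2 counts screen failures within the 25% loss.

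**The case against.** The case for leaving the plan alone has several parts.

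- **No switch effect is promised.** The endpoint itself is worded neutrally as a change, it is exploratory, and the Visit 1 to Visit 2 change has no test. This stands. A reader might infer that the plan claims to isolate the effect of switching; the documents do not say so. What remains is the efficacy label over a change that cannot bear it in group (a).
- **Something does change in group (a).** Patients receive trial-supplied tablets, a fixed morning intake time, tablet counts with an 80% to 120% rule, and lifestyle counselling. Better adherence to ZOF or NEB would be a real drug effect. This also stands. It would be too strong to say that nothing changes, or that no part of the fall could come from the drug. The narrower statement holds: no drug is newly started, and the design cannot separate an adherence gain from regression to the mean.
- **Both groups are shown, so a reader can subtract.** This holds only for the unadjusted difference, which takes no account of Visit 1 pressure or drug class, and in the safety population it would inherit the Visit 2 filter.
- **The groups are not randomised.** Group (a) was uncontrolled on ZOF or NEB, group (b) on other agents, so drift cancels only so far as usual BP and variability are alike. ANCOVA does not cure this. It stands as a limit on what the contrast can show.
- **The contrast is imprecise.** This stands; the half-widths exceed the enrolled DBP drift at issue.

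**Conclusion.** The point holds in a limited form. The plan puts the run-in change under antihypertensive efficacy, but in continuing patients it measures drift on an existing drug. The same kind of drift sits inside the switched patients' change, no contrast is planned, and the stated populations conflict.

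The expected drift in enrolled patients is 0.4 to 2.2 mmHg DBP and 0.8 to 3.7 mmHg SBP, all of it resting on assumed usual pressures and variability. In the safety population the fall may shrink or vanish, depending on how the Visit 2 threshold is read.

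A reader might go on to infer that this undermines the primary result, or that group (a)'s change should be a benchmark for the 2 mmHg null in the sample size. Neither follows. The primary endpoint is the Visit 2 to Visit 3 change and does not use these data. The selection thresholds at Visit 1 and Visit 2 also differ, so drift after one does not measure drift after the other.

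**What to change.** In SAP 16.3.1 and 16.3.2:

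1. Describe group (a)'s Visit 1 to Visit 2 change as change on continued same-drug therapy: a reference, not efficacy.
2. Analyse the Visit 1 to Visit 2 change in all Enrolled patients with a Visit 2 reading, in line with protocol 14.4, and reconcile protocol 14.5.5 with it.
3. Add switched minus continued for DBP and SBP with a 95% CI, by ANCOVA on the Visit 1 value with drug class (ACE-i to ZOF, BB to NEB) as a factor. SAP 7.1 says "No adjustment for covariates will be performed for this study", so record this as a stated exception.
4. Label the contrast exploratory and non-randomised.

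The cost is SAP wording, an aligning correction to the protocol text, and one table from data already collected. The downside is a wide interval that will often be inconclusive, which the table should show plainly.

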#### **Protocol Template**

Sponsor: Menarini Pharmaceutical Study Code: MEIN/19/ZoNe-HYP/001

Protocol Version\_1 of 16/07/2020

patient will be considered eligible to be enrolled in the study only if he/she meets all of the inclusion criteria and none of the exclusion criteria.

#### Inclusion criteria:

- Male or female Caucasian uncontrolled hypertensive patients (see definition in criterion 3) ≥18 and <65 years of age, in monotherapy either with ACE-i or BBs since at least 1 month, at Screening (Visit 1)
- 2. Patients are able to understand and have freely given written informed consent at Screening
- Patients with mean sitting SBP ≥140 mmHg and ≤179 mmHg and/or mean sitting DBP ≥ 90 mmHg and ≤109 mmHg at Screening (Visit 1)
- 4. Patient who are able to comply with all study procedures and who are available for the duration of the study
- Ability to take oral medication and willing to adhere to the drug regimen
- 6. A female patient of childbearing potential is eligible to participate if she is not pregnant, or not breastfeeding. A woman is considered fertile following menarche and until becoming postmenopausal unless permanently sterile. Women of childbearing potential must agree to use of highly effective contraception (eg, method of birth control throughout the study period and for 4 weeks after study completion defined as a method which results in a failure rate of less than 1% per year) and also must refrain from donating or storing eggs during this time. Highly effective contraception methods can be:
  - Combined (estrogen- and progestogen-containing) hormonal contraception associated with inhibition of ovulation (oral, intravaginal, transdermal)
  - Progestogen-only hormonal contraception associated with inhibition of ovulation (oral, injectable, implantable)

Identification Number: FORM-000050125

Previous Doc Number:
CTWI10A

Version Number: 1.0, CURRENT

### **Protocol Template**

Sponsor: Menarini Pharmaceutical Study Code: MEIN/19/ZoNe-HYP/001

Protocol Version\_1 of 16/07/2020

- Intrauterine device (IUD)
- Intrauterine hormone-releasing system (IUS)
- Bilateral tubal occlusion
- Vasectomized partner (provided that partner is the sole sexual partner of the trial participant and that the vasectomized partner has received medical assessment of the surgical success)
- 7. A male patient with female partner must agree to use contraception during the whole study period and for at least 1 week after the last dose of study treatment and refrain from donating sperms during this period.

#### **Exclusion criteria:**

Patients who meet any of the following criteria will not qualify for entry into the study:

- Known contraindications, allergies, or hypersensitivities to any of the study medications or excipient as outlined in the investigators brochures (IBs), summary of product characteristics (SmPCs) or local package inserts for NEB and ZOF
- 2. Patients with serious disorders (in the opinion of the Investigator) which may limit the ability to evaluate the efficacy or safety of the tested medications, including cerebrovascular, cardiovascular, renal, respiratory, hepatic, gastrointestinal, endocrine/ or metabolic, hematological, or oncological, neurological, and psychiatric diseases. The same applies for immunocompromised and/or neutropenic patients
- 3. Patients having a history of the following within the last 6 months: myocardial infarction, unstable angina pectoris, percutaneous coronary intervention, bypass surgery, heart failure, hypertensive

Identification Number: FORM-000050125

Previous Doc Number:
CTWI10A

Version Number: 1.0, CURRENT

#### **Protocol Template**

Sponsor: Menarini Pharmaceutical Study Code: MEIN/19/ZoNe-HYP/001

Protocol Version\_1 of 16/07/2020

- encephalopathy, cerebrovascular accident (stroke), or transient ischemic attack

  4. Patients with secondary hypertension of any etiology such as renal diseases, pheochromocytoma, or Cushing's syndrome

  5. Patients with severe heart failure (New York Heart Association classification III-IV), a narrowing of the aortic or bicuspid valve, an obstruction of cardiac outflow (obstructive, hypertrophic cardiomyopathy) or symptomatic coronary disease

  6. Patients with clinical evidence of renal disease as per the Investigator's judgement (including renovascular occlusive disease, nephrectomy and/or renal transplant, bilateral renal artery stenosis or
  - 7. History of angioneurotic edema

impairment)

- 8. Patients with clinically relevant hepatic impairment
- 9. Patients with sick sinus syndrome, including sino-atrial block
- 10. Patients with second- or third-degree heart block (without a pacemaker)

unilateral renal artery stenosis in a solitary kidney, or severe renal

- 11. History of bronchospasm and bronchial asthma
- 12. Patients with bradycardia (heart rate <60 bpm)
- 13. Patient with metabolic acidosis
- 14. Patients with severe peripheral circulatory disturbances
- 15. Participation in another study within the last 4 weeks
- 16. Patients with diseases that, in the opinion of the Investigator, prevent a careful adherence to the protocol
- 17. Pregnant and breastfeeding women. NOTE: a pregnancy test will be performed on all women of childbearing potential at each study visit

Clinical Sites

15 investigational clinical sites

Identification Number: FORM-000050125

Previous Doc Number: CTWI10A

Version Number: 1.0, CURRENT

